### **13.3 Methods for Evaluation of Measurable Disease**

All measurements should be taken and recorded in metric notation using a ruler or calipers. All baseline evaluations should be performed as closely as possible to the beginning of treatment and never more than 30 days before the beginning of the treatment.

The same method of assessment and the same technique should be used to characterize each identified and reported lesion at baseline and during follow-up. Imaging-based evaluation is preferred to evaluation by clinical examination when both methods have been used to assess the antitumor effect of a treatment.

Clinical lesions: Clinical lesions will only be considered measurable when they are superficial (e.g., skin nodules and palpable lymph nodes). In the case of skin lesions, documentation by color photography, including a ruler to estimate the size of the lesion, is recommended.

Chest x-ray: Lesions on chest x-ray are acceptable as measurable lesions when they are clearly defined and surrounded by aerated lung. However, CT is preferable.

Conventional CT and MRI: These techniques should be performed with cuts of 10 mm or less in slice thickness contiguously. Spiral CT should be performed using a 5 mm contiguous reconstruction algorithm. This applies to tumors of the chest, abdomen, and pelvis. Head and neck tumors and those of extremities usually require specific protocols.

Ultrasound (US): When the primary endpoint of the study is objective response evaluation, US should not be used to measure tumor lesions. It is, however, a possible alternative to clinical measurements of superficial palpable lymph nodes, subcutaneous lesions, and thyroid nodules. US might also be useful to confirm the complete disappearance of superficial lesions usually assessed by clinical examination.

Endoscopy, Laparoscopy: The utilization of these techniques for objective tumor evaluation has not yet been fully and widely validated. Their uses in this specific context require sophisticated equipment and a high level of expertise that may only be available in some centers. Therefore, the utilization of such techniques for objective tumor response should be restricted to validation purposes in reference centers. However, such techniques may be useful to confirm complete pathological response when biopsies are obtained.

Tumor markers: Tumor markers alone cannot be used to assess response. If markers are initially above the upper normal limit, they must normalize for a patient to be considered in complete clinical response.

Cytology, Histology: These techniques can be used to differentiate between partial responses (PR) and complete responses (CR) in rare cases (e.g., residual lesions in tumor types, such as germ cell tumors, where known residual benign tumors can remain). The cytological confirmation of the neoplastic origin of any effusion that appears or worsens during treatment when the measurable tumor has met criteria for response or stable disease is mandatory to differentiate between response or stable disease (an effusion may be a side effect of the treatment) and progressive disease.

## 13.4 Response Criteria

### 13.4.1 Evaluation of Target Lesions

Complete Response (CR): Disappearance of all target lesions. Lymph node CR is when the lymph node has decreased to less than 10mm in the short axis.

Partial Response (PR): At least a 30% decrease in the sum of the longest diameter (LD) of target lesions, taking as reference the baseline sum LD.

Progressive Disease (PD): At least a 20% increase in the sum of the LD of target lesions, taking as reference the smallest sum LD recorded since the treatment started (including the baseline scan if that is the smallest), and at least a 5mm increase or the appearance of new lesions.

Stable Disease (SD): Neither sufficient shrinkage to qualify for PR nor sufficient increase to qualify for PD, taking as reference the smallest sum LD since the treatment started.

## 13.5 Evaluation of Non-Target Lesions (see Table 15)

Complete Response (CR): Disappearance of all non-target lesions and normalization of tumor marker level

Note: If tumor markers are initially above the upper normal limit, they must normalize for a patient to be considered in complete clinical response.

Incomplete Response (SD): Persistence of one or more non-target lesion(s) and/or maintenance of tumor marker level above the normal limits.

Progressive Disease (PD): Appearance of one or more new lesions and/or unequivocal progression of existing non-target lesions. However, unequivocal progression should not normally trump target disease status. It must be representative of overall disease status change, not a single lesion increase.

Although a clear progression of non-target lesions only is exceptional, the opinion of the treating physician should prevail in such circumstances.

### **13.5.1 Evaluation of Best Overall Response**

The best overall response is the best response recorded from the start of the treatment until disease progression/recurrence (taking the smallest measurements recorded since the treatment started as reference for progressive disease). The patient's best response assignment will depend on the achievement of measurement criteria, but confirmation is not necessary.

**Table 15: Assessment of Best Overall Response Using Target and Non-Target Lesions**

Target Lesions	Non-Target Lesions	New Lesions	Overall Response
CR	CR	No	CR
CR	Non-CR/Non-PD	No	PR
PR	Non-PD	No	PR
SD	Non-PD	No	SD
PD	Any	Yes or No	PD
Any	PD*	Yes or No	PD
Any	Any	Yes	PD

\* In exceptional circumstances, unequivocal progression in non-target lesions may be accepted as disease progression.

Note : Patients with a global deterioration of health status requiring discontinuation of treatment without objective evidence of disease progression at that time should be reported as —symptomatic deterioration”. Every effort should be made to document the objective progression even after discontinuation of treatment.

### **13.6 Duration of Response**

Duration of overall response: The duration of overall response is measured from the time measurement criteria are met for CR or PR (whichever is first recorded) until the first date that recurrent or progressive disease is objectively documented (taking as reference for progressive disease the smallest measurements recorded since the treatment started).

Duration of stable disease: Stable disease is measured from the start of the treatment until the criteria for progression are met, taking as reference the smallest measurements recorded since the treatment started.

### **13.7 Progression-free Survival**

Progression-free survival is determined programmatically from adjudicated PD, defined as the interval from the start of treatment until the first date on which recurrence, progression (per RECIST v1.1) or death due to any cause, is documented, censored at the last assessable evaluation, or at the initiation of new anticancer therapy. It is not necessary to confirm disease progression.

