## Experimental Design Schema

	Pre-Study (up to 28 days prior to enrolling) i	Cycle 1 Day 1 (28 day cycle)	Cycle 1 Day 8 (± 1 day)	Cycle 1 Day 15 (± 1 day)	Cycle 2 Day 1 (± 3 days)	Cycle 2 Day 15 (± 3 days)	Cycle 3 Day 1 (± 3 days)	Cycle 4 Day 1 (± 3 days)	Cycle 5 Day 1 (±3 days)	Cycle 6 Day 1 (±3 days)	Every Cycle Thereafter (± 3 days)	Every 3 cycles (±7 days)	Off treatment h
Neratinib (day 1-28 every 4 weeks a,b )		X	X	X	X	X	X	X	X	X	X		
Demographics	X												
Medical history	X												
Concurrent meds (± 1 wk)	X	X			X		X	X	X	X	X		X
Physical exam (± 1 wk)	X	X			X		X	X	X	X	X		X
Vital signs (± 1 wk)	X	X			X		X	X	X	X	X		X
Height	X												
Weight (± 1 wk)	X	X	X	X	X	X	X	X	X	X	X		X
Performance Status (± 1 wk)	X	X			X		X	X	X	X	X		X
CBC w/diff, plts (± 1 wk)	X	X			X		X	X	X	X	X		X
Complete Metabolic Panel c (± 1 wk)	X	X	X	X	X	X	X	X	X	X	X		X
Diarrhea Checklist		X l											
Nurse brief toxicity evaluation		X	X	X	X	X	X						
EKG	X												
Pharmacokinetic samples j				X			X	X					
Adherence evaluation (pill count, diaries) (± 1 wk)		X	X	X	X	X	X	X	X	X	X		
Adverse event evaluation (± 1wk)		X	X	X	X	X	X	X	X	X	X		X
Tumor measurements using CT or PET-CT (± 1 wk)	X d							X				X e	X f
LVEF Assessment	X d							X e				X e	X f

Geriatric Assessment Survey( $\pm 1$ wk) k	X						X					X g
Peripheral Blood Correlatives k	X						X					X
Bacteriomic profiling	X m			X	X	X	X					

a: Dose as assigned; neratinib 240mg orally daily; Doses held due to toxicity will not be made up.

b: If baseline laboratory tests are done within 14 days of start of treatment, these labs do not need to be repeated prior to Day 1.

c: Albumin, alkaline phosphatase, total bilirubin, bicarbonate, BUN, calcium, chloride, creatinine, glucose, potassium, total protein, SGOT[AST], SGPT[ALT], sodium.

d: Baseline assessment may be done up to 30 days prior to study enrollment.

e: Tumor measurements and LVEF assessment are repeated every 3 cycles  $\pm 1$  wk until patient comes off study. Documentation (radiologic or clinical) must be provided for patients removed from study for progressive disease.

f: Off-study radiologic evaluation will only be done if clinically indicated.

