## 7.5 Subject Follow-Up

Throughout the study, reconciliation will be made between the amount of investigational product supplied, dispensed, returned, and subsequently destroyed or returned to IDS pharmacy. All investigational products that were supplied by the sponsor will be returned to IDS pharmacy, or destroyed at the site in accordance with COH guidelines. Individual patient dosing compliance should be reviewed at each study visit by study site staff. If patient non-compliance is noted, the patient should be re-instructed regarding proper dosing procedures in order to continue in the study. If repeated non-compliance is noted, additional steps may be taken, including withdrawal of the patient from the study. Subjects will be followed for toxicity outcomes for an additional 30 days after stopping the drug and until resolution of all grade  $>2$  toxicities. Patients removed from study for unacceptable adverse events will be followed until resolution or stabilization of the adverse event, even after disease progression is noted. All patients will be passively followed until death, though active follow-up will cease upon removal from study.

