## 7.6 Supportive Care, Other Concomitant Therapy, Prohibited Medications

All concomitant treatments, therapies and medications will be captured from the signing of the ICF until the end of the treatment. This will include the start date, stop date, generic name, route of administration, dose and indication for treatment. At screening, patients will be asked what medications they have taken during the last 30 days, which medications are ongoing at the time of screening, any medical conditions that require medication, and all prior cancer therapies. At each subsequent study visit, patients will be asked what concomitant medications they are currently taking.

All concomitant medications taken during the study treatment will be recorded in the Case Report Form. The minimum requirements are drug name and dates of administration. All prescription and over-the-counter medications that have been taken within one month prior to the first dose of investigational treatment should also be reported in the Case Report Form. Patients should receive full supportive care during the study, including treatment with antibiotics, antiemetics, blood transfusions, antidiarrheals, and analgesics as appropriate, with the exception of drugs listed in **Section 7.6.3 and 7.6.4**.

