#### 7.7 Laboratory Studies/Monitoring Studies

##### **7.7.1 Required Clinical, Laboratory and Disease Evaluation at Baseline**

Complete blood count and differential, comprehensive metabolic panel (including sodium, potassium, chloride, bicarbonate, blood urea nitrogen, creatinine, glucose, calcium, ALT, AST, alkaline phosphatase, total bilirubin, total protein, and albumin), must be performed within 14 days of enrolling on trial.

A full history and physical exam including demographics, medical history, concurrent medications, vital signs, height measurement, weight measurement, and performance status analysis must be done within one week of enrolling on trial.

Radiologic evaluation including computed tomography (CT) of the chest, abdomen, and pelvis; or combined PET-CT with a diagnostic CT component, must have been performed within 30 days of study enrollment. If measurable disease is present, tumor measurements must be performed and reported from this scan. Central review is not required for treatment decisions in individual subjects.

The patient must complete a Geriatric Assessment prior to starting therapy (see Appendix I). If patient's native language was not covered by the current language forms, Geriatric assessment form can be omitted with clear documentation.

Cardiac imaging (either by echocardiogram or MUGA scan) with a reported left ventricular ejection fraction must be obtained within 30 days of study enrollment. Regardless of where the baseline evaluation is performed, future cardiac evaluation must be performed using only the

same modality as the baseline evaluation. A baseline EKG before starting treatment is also required.

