#### 7.7.3.4 *Survival Status*

Patients will be followed indefinitely to establish overall survival. All participants enrolled on the study will be informed that their medical condition will be followed indefinitely. In order to obtain survival status on the enrolled patients we will need the patient's first and last name, middle initial, social security number, date of birth, and gender. This information will be securely transferred to the primary coordinating institution (City of Hope) and will be kept in a separate password protected file, which will only be linked for the purpose of establishing survivor status. The investigators will utilize the Social Security Death Index and the National Death Index to establish survival status. Survival analysis will be conducted once a year.

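### PFS counts a death however long after the last scan, and no section provides for the therapy date that should censor earlier, so some patients who stop early get a PFS equal to their survival

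*Combined protocol and SAP*

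**What the plan says.** Section 13.7 measures PFS from the start of treatment to the first recurrence, RECIST progression or "death due to any cause, is documented, censored at the last assessable evaluation, or at the initiation of new anticancer therapy". It takes progression from adjudicated progressive disease. Section 15.3 estimates PFS by Kaplan-Meier and also plans a 16-week PFS rate.

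Other sections determine which dates will exist to feed that rule:

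- **Scans.** Every 12 weeks until the patient comes off study. After that, footnote f of the Experimental Design Schema says "Off-study radiologic evaluation will only be done if clinically indicated".
- **Follow-up.** Section 7.5: "All patients will be passively followed until death, though active follow-up will cease upon removal from study".
- **Deaths.** Section 7.7.3.4 follows survival indefinitely: "The investigators will utilize the Social Security Death Index and the National Death Index to establish survival status".
- **Therapies.** Section 7.6: "All concomitant treatments, therapies and medications will be captured from the signing of the ICF until the end of the treatment". Table 16 lists Off Treatment and Follow up/Survival forms, but nothing says that they record later anticancer therapy.
- **Clinical progression.** Footnote e: "Documentation (radiologic or clinical) must be provided for patients removed from study for progressive disease". Section 7.4 instead lists clinical progression confirmed by imaging as a reason for removal.
- **Adjudication.** No process is described. The only remark on central review, in Section 7.7.1, is "Central review is not required for treatment decisions in individual subjects".

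**The concern.** After a patient comes off study, death is actively sought and progression is not scheduled to be looked for. Section 13.7 has one safeguard against late deaths, which is censoring at new anticancer therapy. That safeguard needs a date which no section says will be collected.

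The two kinds of early leaver are then treated differently. One who dies before the analysis has an event at death, possibly years after the last scan. One who is alive is censored at the last scan. Section 13.7 also does not say whether a late death or the last assessable evaluation takes precedence, so two programmers could produce different curves from the same data.

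Patients who stop for toxicity are the main route into this gap. Table 7 and Section 8.0 require permanent discontinuation for several adverse-event patterns. More toxicity stops would therefore lengthen apparent PFS, and the planned exposure-response analyses of efficacy could pick up that link.

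**Working it through.** The plan gives no design figure for PFS, so there is none to reproduce. The check has three parts.

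**1. The single patient.** Section 4.0 expects on average 9.5 months of treatment and 38 months of long-term follow-up. A patient on those averages who stops without documented progression, has no later scan or recorded therapy, and dies at the end of follow-up has PFS = 9.5 + 38 = 47.5 months, which equals OS.

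**2. The trial-level illustration.** Inputs from the documents:

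- median PFS 22.3 weeks (Section 1.4.6.1, patients with prior trastuzumab)
- scans every 12 weeks (Section 13.1)
- 30-month accrual and a 48-month study (Section 15.1)

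Assumed inputs: 6% to 30% of patients stop for toxicity, uniformly over weeks 2 to 16; median OS 78 to 104 weeks; no later scan and no therapy date on file. The only anchor for the stopping rate is 6.1% stopping for diarrhea in pooled data (Section 1.4.5.4).

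An exponential model fits the source study tolerably: 0.5^(16/22.3) = 0.61 at 16 weeks, against 59% reported. Progression here is seen only at 12-week scans, so the fully ascertained curve is about 0.5^(12/22.3) = 0.69 at week 16 and 0.5^(48/22.3) = 0.225 at week 52.

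If every death is captured, the 52-week value can be worked by hand:

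- Share q leaving before documented progression, for stopping rate f: q ≈ f × (10/14 + 4/14 × 0.69) = 0.91f.
- Survival at 52 weeks: (a·e^(−52b) − b·e^(−52a))/(a − b), with a = ln 2/22.3 = 0.0311 and b = 1/63 or 1/99.6 (mean weeks from progression to death that give median OS 78 or 104). This gives 0.69 and 0.78.
- Apparent 52-week PFS ≈ 0.225 + q × (OS at 52 weeks − 0.225). At f = 20%: 0.225 + 0.182 × 0.463 = 0.309, and 0.225 + 0.182 × 0.556 = 0.326.

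With a 48-month cutoff and living leavers censored at their last scan, simulation is needed. Kaplan-Meier estimates:

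| Stop for toxicity | 16-week PFS, cutoff | 52-week PFS, cutoff | 52-week PFS, every death captured |
|---|---|---|---|
| none (true) | 69% | 22% | 22% |
| 6% | 69–70% | 24% | 25% |
| 10% | 70% | 25% | 27–28% |
| 20% | 71% | 27–28% | 31–33% |
| 30% | 72–73% | 30–31% | 35–38% |

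If the new-therapy date were on file for every leaver (assumed 4 weeks after stopping), 52-week PFS would be about 23%. With deaths more than 26 weeks after the last evaluation censored at that evaluation, it is 21 to 22% and the median is 24 weeks, as under full ascertainment.

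**3. A second model.** Here progression is dated exactly, leaving is spread over 36 weeks, mean survival after leaving is 12 to 38 months, and the cutoff is 48 months.

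- Leavers who die by cutoff get a median PFS of 46 to 66 weeks, against 38 weeks true.
- The trial median is 22.4 to 23.0 weeks against 22.3. The 52-week PFS is 0.20 to 0.23 against 0.20.
- A 24-week limit on deaths errs slightly the other way in this model: median 20.5 to 22.0 weeks, 52-week PFS 0.17 to 0.20.
- With leaving confined to the first 12 weeks, every death captured and 38 months' mean survival, the median reaches 23.4 to 29.2 weeks.

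**The case against.** Several stronger readings are tempting, and the documents do not support them.

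- **That scans stop with treatment.** Only scheduled scans stop, and footnote e ties that to coming off study. Clinically indicated scans may follow. The note to Table 15 asks for every effort to document objective progression after discontinuation, though only for symptomatic deterioration. The illustration assumes that no later scan finds anything, which is a worst case.
- **That a patient who stops, starts another line and dies much later is credited with PFS until death.** As written, Section 13.7 censors that patient at the new line. The long PFS follows only if the date is missing. Section 7.6 concerns concomitant medication, the calendar marks concurrent medications at the off-treatment visit, and the fields of the follow-up forms are not shown. What can be said is that collection is not provided for, not that it will not happen.
- **That everyone removed for clinical progression falls into the gap.** Section 7.4 words that criterion as confirmed by imaging. The gap is limited to patients with clinical documentation only, which footnote e allows.
- **That stopping for toxicity is the expected outcome.** The endpoint is grade 2 or higher toxicity. Section 10.2.1 expects prophylaxis to reduce discontinuation, and in the phase 2 study in Section 1.4.6.1 one patient stopped for diarrhea.
- **That the median is badly inflated.** In the first model it can move from 24 to as much as 36 weeks, but that is partly the 12-week scan grid: the true curve is already near 0.5 at week 24. The second model moves it by under 1 week at a 48-month cutoff.

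What survives is the open-ended death rule, the unsupplied therapy date, the unstated precedence and the undefined adjudication.

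**Conclusion.** The point holds as a gap in definition and data collection, with a modest upward bias in a secondary endpoint. For an affected patient the distortion is complete: PFS equals OS.

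For the trial, at a 48-month cutoff and with no therapy dates on file, 52-week PFS is raised by about 2 points at 6% stopping, 3 at 10%, 5 to 6 at 20% and 8 to 9 at 30%. The 16-week rate rises by at most about 4 points. For scale, the binomial standard error at 22.5% with 40 patients is √(0.225 × 0.775/40) = 6.6 points. At low stopping rates the bias is well inside sampling error; at 30% it exceeds one standard error.

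No PFS cutoff is stated and survival is analysed yearly, so later updates would drift toward the every-death figures. All of this rests on assumed stopping rates, stopping times and survival, and on no progression being found after stopping. If therapy dates were recorded, most of the 52-week bias would disappear. The primary toxicity result is unaffected.

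**What to change.** 1. Add the start date of first subsequent anticancer therapy to the Off Treatment and Follow up/Survival forms in Table 16, so that the censoring rule in Section 13.7 can be applied. Record any routine-care scan done after stopping.
2. In Section 13.7, state the precedence of events and censoring. Censor a death that falls more than two scheduled scan intervals (24 weeks plus 2 weeks of windows, about 26 weeks) after the last assessable evaluation at that evaluation, counting baseline if there is no later scan. Keep death at any time as an event in a sensitivity analysis.
3. Replace adjudicated progression with investigator-assessed RECIST 1.1 progression, or describe the adjudication.
4. Add a supportive analysis that counts clinical progression without imaging, symptomatic deterioration or new anticancer therapy as events. Footnote e and Section 7.4 must be reconciled.

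The cost is wording in Sections 13.7 and 15.3, one date field, entry of scans already done, and two extra Kaplan-Meier runs. No scans are added. The two-interval limit is a convention, and reported PFS may be slightly lower. Patients who stop early with only a baseline scan and survive past the limit are censored at the start. In the first model about (10/14)/0.91 = 78% of toxicity leavers have only a baseline scan, so at 20% stopping up to about 40 × 0.182 × 0.78 ≈ 6 patients are exposed to this. That is why the sensitivity analysis belongs beside the main one. The therapy date is easiest to collect prospectively, so item 1 should come first.
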